#### **10.4.3.2 Primary Safety Endpoint**

The following sensitivity analyses will be performed in the SP.

1) *Best-Case Scenario*

Subjects with missing safety outcome will be treated as free from primary adverse events. The point estimate for freedom from early onset primary adverse events and the corresponding exact two-sided 95% confidence interval will be presented.

2) *Worst-Case Scenario*

Subjects with missing safety outcome will be treated as having experienced a primary adverse event. The point estimate for freedom from early onset primary adverse events and the corresponding exact two-sided 95% confidence interval will be presented.

3) *Tipping Point Analysis*

In this study, the tipping point is defined as the number of subjects with primary AEs for the binary safety endpoint in the study population at which the study conclusion is changed. The tipping-point analysis will replace the missing values with primary AE occurrence one at a time and the corresponding Z test statistic will be produced. If the Z value is equal to or greater than  $Z_{\alpha/2}$ , the resulting imputed number of primary AE is the tipping point. The significance level will be set at 0.05.

The tipping-point analysis for binary safety endpoints will analyze all possible cases that may occur in the missing data cohort. The results will be presented in a summary table to illustrate how Z statistic and conclusion on meeting performance goal changes. As listed below, additional analyses may also be performed to assist clinical judgment on whether such a tipping point is implausibly unfavorable.

4) *Additional analyses:*

- The demographic and baseline characteristics will be compared between the observed data cohort and missing data cohort. Fisher' exact test will be used for binary variables and Krustal-Wallis test will be used for continuous outcomes as appropriate.
- The reasons for missingness, if available, will be listed for missing data by site.

#### **10.4.4 Subgroup Analysis**

##### **10.4.4.1 Site Heterogeneity**

Each site should enroll no more than 15% of the total enrollment to minimize the possibility that the study results could be highly influenced by a few sites. Sites with less than five subjects will be combined according to geographic regions. Using this pre-determined criterion, sites with less than five subjects within the same geographic region will be combined such that the combined center(s) would have five or more subjects and no more than 5 sites combined.

A Chi-square test will be used to examine the homogeneity across sites for the primary effectiveness and safety endpoints. A p-value less than 0.15 will be considered statistically significant for an assessment of heterogeneity across sites. A non-significant result will support pooling of sites for the primary analyses.

If the sites are not poolable, logistic regression models treating site as a random effect will be fit to examine the impact of site heterogeneity on the primary endpoints. This logistic regression will be used as sensitivity analyses.

##### **10.4.4.2 Region Heterogeneity**

Approximately 30 US sites and 5 OUS (outside of US) sites will be involved in this study. Up to 30% of subjects may be enrolled at OUS sites and approximately 70% of subjects enrolled at US sites.

A Chi-square test will be used to examine the heterogeneity between regions (US vs OUS) for the primary effectiveness and safety endpoints. A p-value less than 0.15 will be considered

statistically significant for an assessment of heterogeneity between regions. A non-significant result will support pooling of regions for the primary analyses.

If the regions are not poolable, logistic regression models treating region as a random effect will be fit to examine the impact of region heterogeneity on the primary endpoints. This logistic regression will be used as sensitivity analyses.

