#### **10.4.4.3 Subgroup Analysis by Sex**

In order to reflect the sex ratio of the intended population, Biosense Webster plans to enroll approximately 70% male subjects and 30% female subjects in the study.

Fisher's exact test will be conducted to examine differences in primary safety and effectiveness rates by sex. A p-value less than 0.15 will be considered statistically significant for an assessment of the rate differences by sex. If the test results demonstrate differences by sex, the effectiveness success rate and/or primary AE event rate overall and the 95% confidence intervals will be summarized for each sex group. A logistic regression model treating sex as a fixed effect will be fit to examine the impact of sex on the primary endpoint controlling for covariates.

These analyses will be performed in the PP population for the primary effectiveness endpoint and in the SP for the primary safety endpoint

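### SAP 10.4.4.2 fits a two-level factor, US versus OUS, as a random effect, so the follow-up to a positive regional test does not estimate the regional difference

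*SAP*

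**What the plan says.** SAP 10.4.4.2 plans that "A Chi-square test will be used to examine the heterogeneity between regions (US vs OUS) for the primary effectiveness and safety endpoints". The threshold for heterogeneity is p<0.15. If the regions are judged not poolable, "logistic regression models treating region as a random effect will be fit to examine the impact of region heterogeneity on the primary endpoints". The section gives the model's status: "This logistic regression will be used as sensitivity analyses". It names no fixed region term, no regional rates with intervals, and no particular output of the model to be read.

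On the regions themselves it says: "Approximately 30 US sites and 5 OUS (outside of US) sites will be involved in this study", and "Up to 30% of subjects may be enrolled at OUS sites and approximately 70% of subjects enrolled at US sites".

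Two neighbouring sections help in reading this one. SAP 10.4.4.1 uses the same random-effect approach for site, where there may be up to 35 levels. SAP 10.4.4.3 deals with sex, the other two-level factor, with the same 0.15 threshold: "A logistic regression model treating sex as a fixed effect will be fit to examine the impact of sex". If the sexes differ, it also summarises rates and 95% CIs for each sex.

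**The concern.** A random effect suits a factor with many levels that can be treated as a sample from a larger set. Site fits that description. US and OUS do not: they are two specific groups, and the question is how far apart they are.

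The model runs only after the data have suggested a regional difference. At that point the reader needs the rate in each region and the difference with its uncertainty. The planned model supplies a variance estimated from two values and predictions shrunk towards a common mean. It could make a flagged difference look negligible, or return an interval for the overall rate so wide that it says little about robustness.

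**Working it through.** **1. Inputs.** SAP 9.1 and 9.3 give 330 evaluable subjects, and 330/0.90 = 366.7, rounded up to the stated 367. SAP 10.4.4.2 contains no numerical result to reproduce. Taking the 70/30 split gives 0.70 × 330 = 231 US and 0.30 × 330 = 99 OUS. The 30% is a ceiling, so 99 is the largest planned OUS group. Regional success counts are assumptions.

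**2. The two models.**
- SAP: logit(p_r) = β + u_r, with u_r ~ N(0, σ²) and r = US, OUS. The parameters are β and σ.
- Fixed effect: logit(p_r) = β + δ × [r = OUS]. Here δ is the regional difference on the log-odds scale.

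Only the second has a parameter for the quantity of interest.

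**3. What two levels say about σ.** Even if the two regional effects were observed without error, the normal-theory 95% CI for an SD on 1 df is s/√5.024 to s/√0.000982, or 0.45s to 32s.

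**4. Worked examples.** The random-effect model was fitted by maximum likelihood with Gauss-Hermite quadrature. Its interval for the overall rate is a Wald interval with σ held at its estimate. Pooled intervals are Clopper-Pearson. The difference is p_US − p_OUS ± 1.96 × √[p_US(1−p_US)/231 + p_OUS(1−p_OUS)/99].

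| | 109/231, 56/99 | 106/231, 59/99 | 127/231, 40/99 |
|---|---|---|---|
| Observed US, OUS | 47.2%, 56.6% | 45.9%, 59.6% | 55.0%, 40.4% |
| Chi-square p | 0.12 | 0.022 | 0.015 |
| Estimated σ (logit) | 0.03 | 0.21 | 0.24 |
| Predicted US, OUS (random effect) | 49.9%, 50.2% | 47.5%, 55.9% | 53.5%, 43.9% |
| Pooled rate (exact 95% CI) | 50.0% (44.5-55.5) | 50.0% (44.5-55.5) | 50.6% (45.1-56.1) |
| Random-effect overall rate (95% CI) | 50.1% (44.6-55.6) | 51.7% (42.4-60.9) | 48.7% (38.8-58.6) |
| Difference US − OUS, points (95% CI) | −9.4 (−21.1 to +2.3) | −13.7 (−25.3 to −2.1) | +14.6 (+3.0 to +26.2) |

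For the last column, the standard error is √(0.550 × 0.450/231 + 0.404 × 0.596/99) = 0.0592, and 14.6 ± 1.96 × 5.92 gives +3.0 to +26.2.

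Observed gaps of 9.4, 13.7 and 14.6 points are predicted as less than half a point, 8.4 and 9.6. In the last column the random-effect interval is 58.6 − 38.8 = 19.8 points wide, against 56.1 − 45.1 = 11.0.

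**5. Dependence on the estimator.** In the first example the log-odds are ln(109/122) = −0.113 and ln(56/43) = 0.264, a gap of 0.377. The variance of that gap is 1/109 + 1/122 + 1/56 + 1/43 = 0.0585. A simple moment estimate of σ² is (0.377² − 0.0585)/2 = 0.042, so σ is about 0.20, against 0.03 by maximum likelihood. The SAP names no estimation method.

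**6. Simulation, restricted to trials that trigger the model.** There were 1,500 trials per scenario, using profile-likelihood intervals.

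| True US, OUS success (assumed) | p<0.15 | 95% interval for σ includes 0 | Mean width, random effect vs exact pooled (points) |
|---|---|---|---|
| 50%, 50% | 16% | 99% | 29 vs 11 |
| 47%, 57% | 59% | 86% | 41 vs 11 |
| 45.5%, 60.5% | 86% | 62% | 48 vs 11 |
| 54.5%, 39.5% | 86% | 63% | 48 vs 11 |

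For safety (257 US and 110 OUS of 367; true rates 8%/8% or 6.5%/11.5%), the widths were 15-20 points against 6, and the interval for σ included 0 in 85-99%.

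**The case against.** The strongest reply is that nothing decisive depends on this model. Success is judged by the exact pooled CI in SAP 10.4.1 and 10.4.2, and the regression runs only when p<0.15, as a sensitivity analysis. That stands, and it limits the weight of the point.

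Some stronger readings are tempting, and the documents do not support them.

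- **That the model could overturn a successful trial.** In the third example its lower limit (38.8%) falls below 40% while the pooled limit does not. The SAP never tests this model against the performance goal.
- **That it distorts the overall rate.** The SAP does not say the back-transformed intercept will be reported as the effectiveness rate. That intercept describes a typical region, which is a different quantity from the pooled rate. In the simulated effectiveness scenarios the average shift was only about 0 to 2.5 points. The wide interval is the larger problem.
- **That the variance usually collapses to zero when the model is used.** With a true between-region SD of 0.3, it did so in 51% of all simulated trials, but in only 7-8% of those that trigger the model. With no true difference, the triggered share was 21%.
- **That software would return nothing, or that regional results would never be seen.** Software will give a variance and shrunken predictions, and the chi-square test needs the region-by-outcome counts. SAP 10.4.4.4 permits further subgroup analyses, but optionally and without naming region. What is missing is a commitment to regional rates and a difference with intervals.

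**Conclusion.** The point holds as a flaw in a conditional sensitivity analysis. With two named regions, a random effect neither parameterises the difference nor determines the variance usefully. In the assumed examples it shrinks a 9.4-point gap to under half a point, or widens the interval for the overall rate from 11.0 to 19.8 points. The SAP's own treatment of sex shows the better method.

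The primary effectiveness and safety decisions are not affected. The sizes rest on assumed regional counts, a 231/99 split (257/110 for safety) and maximum-likelihood fitting. Another estimator would shrink the first example less, and the SAP does not say which applies. The two-level structure and the missing difference parameter depend on none of these assumptions.

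**What to change.** In SAP 10.4.4.2:

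- Replace the random effect with a fixed effect for region (US versus OUS), in line with SAP 10.4.4.3.
- Prespecify US and OUS rates with exact 95% CIs for the primary effectiveness endpoint and for primary adverse events, and the US-OUS difference with its 95% CI.
- Keep the random effect for site only (SAP 10.4.4.1).

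For the third example the new table would show US 55.0% (48.3-61.5), OUS 40.4% (30.7-50.7) and a difference of +14.6 points (+3.0 to +26.2). There is no need to standardise the overall rate to a 70:30 mix: the OUS share is a ceiling, and near that mix standardising would essentially return the pooled rate.

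The cost is a change of SAP wording and one small table, with no new data.

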#### **10.4.4.3 Subgroup Analysis by Sex**

In order to reflect the sex ratio of the intended population, Biosense Webster plans to enroll approximately 70% male subjects and 30% female subjects in the study.

Fisher's exact test will be conducted to examine differences in primary safety and effectiveness rates by sex. A p-value less than 0.15 will be considered statistically significant for an assessment of the rate differences by sex. If the test results demonstrate differences by sex, the effectiveness success rate and/or primary AE event rate overall and the 95% confidence intervals will be summarized for each sex group. A logistic regression model treating sex as a fixed effect will be fit to examine the impact of sex on the primary endpoint controlling for covariates.

These analyses will be performed in the PP population for the primary effectiveness endpoint and in the SP for the primary safety endpoint

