5.0 TREATMENT DESCRIPTION

The Sponsor's intention is for the enrolled subject population to be as representative as possible of the well-defined study population. Investigators will be encouraged to consecutively evaluate all persistent AF candidates for ablation for participation in the study, and to offer enrollment to all who meet preliminary eligibility criteria.

Centers will be selected for participation in the study based on experience with THERMOCOOL SMARTTOUCH® technology, ablation experience, their capacity to screen and enroll a reasonable number of eligible patients, and ability to perform the required study procedures, according to this protocol. Sponsor will attempt to include a diversified group of investigational sites engaging a variety of academic and private institutions geographically located throughout the US and possibly other regions. The trial may include up to 30% of subjects enrolled at OUS sites and approximately 70% of subjects enrolled at US sites. To ensure generalizability of results and minimize the influence of any single site, no more than approximately 15% of the total enrollment will be allowed at a single site.

Historically, women have been underrepresented in or excluded from many clinical studies, leading to lack of information for women and their physicians regarding the risks and benefits of many medical treatments and diagnostic procedures. It is the Sponsor's intent to apply the principles from FDA's guidance titled Evaluation of Sex-Specific Data in Medical Device Clinical Studies in this clinical trial to ensure adequate representation of women and minorities. The Sponsor will take feasibility steps to ensure adequate representation of women and racial or ethnic minorities in this clinical trial:

In order to reflect the gender ratio of the intended population, Sponsor plans to enroll approximately 70% males and 30% females in the study. The gender ratio (male: female = 7:3) undergoing ablation procedures in the AF population is estimated based on previous studies.⁷⁵

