## **9 Sample Size Justification**

### **9.1 Primary Effectiveness Endpoint**

The primary effectiveness endpoint is freedom from documented atrial tachyarrhythmia recurrence without failure modes during the evaluation period (Day 181-450). A performance goal of 40% is set for the primary effectiveness endpoint. Please refer to Section 4.1 of the protocol for justifications of performance goals for the primary effectiveness endpoint.

Based on a performance goal of 40% and an anticipated freedom from AF recurrence rate of 50%, 330 subjects will be required to obtain at least 90% power at a two-sided significance level of 0.05 using the exact binomial method.

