### **9.2 Primary Safety Endpoint**

The primary safety endpoint is the incidence of any primary adverse event occurring within 7 days of the AF ablation procedure (including the initial and repeat AF ablation procedure) using the study catheter. A performance goal of 16% is set for the primary safety endpoint. Please refer to Section 4.1 of the protocol for justifications of performance goals for the primary safety endpoint.

Based on a performance goal of 16% and an anticipated rate of 8% for the primary safety endpoint, 232 subjects will be required to obtain at least 90% power at a two-sided significance level of 0.05 using the exact binomial method.

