### **9.3 Total Sample Size**

It is estimated that the attrition rate is no more than 10%. In order to obtain 330 subjects, Biosense Webster proposes to enroll 367 ( $=330/0.90$ ) subjects to account for this potential subject attrition.

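### Sex-specific primary endpoint rates and confidence intervals are required only if a Fisher test gives p<0.15, a trigger that a 1.5-fold excess of events in women would miss about 65% of the time

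*SAP*

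**What the plan says.** SAP 10.4.4.3 sets out the sex analysis in three steps.

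- The test: "Fisher's exact test will be conducted to examine differences in primary safety and effectiveness rates by sex".
- The threshold: "A p-value less than 0.15 will be considered statistically significant for an assessment of the rate differences by sex".
- The consequence: "If the test results demonstrate differences by sex, the effectiveness success rate and/or primary AE event rate overall and the 95% confidence intervals" are then summarised for each sex. A logistic model with sex as a fixed effect, adjusted for covariates, comes in the next sentence. That sentence has no condition of its own, so it is unclear whether the model also depends on the test.

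Effectiveness is analysed in the per-protocol (PP) population and safety in the safety population (SP). The same section says the sponsor "plans to enroll approximately 70% male subjects and 30% female subjects in the study".

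Elsewhere, SAP 10.3 gives demographics and baseline characteristics by sex, but no outcomes. SAP 10.4.4.4 makes further subgroup analyses optional. SAP 10.4.5.1 plans univariate logistic models of both primary outcomes for each candidate predictor, naming gender, without reference to the Fisher test. Protocol 5.0 notes the lack of information for women on risks and benefits. It says the sponsor will apply the principles of the FDA guidance on "Evaluation of Sex-Specific Data in Medical Device Clinical Studies in this clinical trial to ensure adequate representation of women and minorities".

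**The concern.** Whether the rate in women is shown with its interval depends on a p-value from a comparison for which the plan states no power. Two things follow. A moderate difference can be real and still leave the report without a rate for women. And when rates are shown because the test was positive, the observed difference tends to exceed the true one.

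The absolute rate matters because both primary endpoints are judged against fixed goals, 40% success and 16% Primary AEs. A reader who wants to know how women stand against those goals needs their rate and its interval. No primary test, error rate or success decision depends on this; what is at stake is the completeness of the report for about 30% of the subjects.

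**Working it through.** **The plan's own figures.** SAP 9.1 plans 330 subjects for a power of 90% or more, with 50% success expected against the 40% goal. Under the exact rule at N=330, at least 151 successes are needed for the lower 95% bound to exceed 40%. P(X ≥ 151 | 330, 0.50) = 94.5%, so the claim is met. SAP 9.2 plans 232 subjects for the same power, with 8% Primary AEs expected against the 16% goal. At N=232 at most 26 events are allowed, and P(X ≤ 26 | 232, 0.08) = 96.8%, also met. SAP 9.3: 330/0.90 = 366.7, rounded up to 367. All three statements hold. None concerns the sex comparison.

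**Inputs.**
- Fisher's exact test at p<0.15 (SAP 10.4.4.3). Sidedness is not stated; taken as two-sided.
- Split 70:30: 0.70 × 330 = 231 men and 0.30 × 330 = 99 women. If all 367 enrolled subjects contribute: 257 and 110.
- Overall rates: 8% Primary AEs (SAP 9.2) and 50% success (SAP 9.1).
- Size of the sex difference: not in the documents. Assumed range: women-to-men risk ratio (RR) 1.5 to 2.5.

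**Probability that the trigger is met.** Holding the overall rate at 8%, the rate in men is p_m = 0.08/(0.7 + 0.3 × RR) and the rate in women is p_w = RR × p_m. For RR = 2: p_m = 0.08/1.3 = 6.2% and p_w = 12.3%. The trigger probability is the sum, over all pairs of counts (x, y), of Bin(x; 231, p_m) × Bin(y; 99, p_w) for pairs with Fisher p<0.15.

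| RR | Men | Women | Triggered, N=330 | Triggered, N=367 |
|---|---|---|---|---|
| 1.5 | 7.0% | 10.4% | 34% | 35% |
| 1.75 | 6.5% | 11.4% | 50% | 52% |
| 2.0 | 6.2% | 12.3% | 64% | 66% |
| 2.5 | 5.5% | 13.8% | 82% | 85% |

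The trigger is therefore missed about 65% of the time at RR 1.5 and about 36% at RR 2.0. With men fixed at 8%, women at 12%, 14% and 16% trigger it 37%, 56% and 73% of the time at N=330 (38%, 58% and 76% at N=367). With 8% in both sexes it triggers 12% of the time.

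For effectiveness at N=330, 50% in men versus 40% in women triggers 58% of the time and so misses 42%. That pair implies 0.7 × 50% + 0.3 × 40% = 47% overall. Holding the overall rate at 50% (53% versus 43%) gives 57%.

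**Selection when triggered.** Averaging the observed difference over triggered outcomes only (N=330), a true 8% versus 12% (4 points) averages 7.7 points. A true 50% versus 40% (10 points) averages 14 points.

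**What the reader would see.** Take 26 events in 330 subjects (26/330 = 7.9%, about the planned rate), with exact 95% intervals for women:

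| Women | Men | Fisher p | Per-sex rates required? | Interval for women |
|---|---|---|---|---|
| 10/99 = 10.1% | 16/231 = 6.9% | 0.37 | No | 5.0–17.8% |
| 11/99 = 11.1% | 15/231 = 6.5% | 0.18 | No | 5.7–19.0% |
| 12/99 = 12.1% | 14/231 = 6.1% | 0.075 | Yes | 6.4–20.2% |

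In the first two rows the upper bound for women lies above the 16% goal, yet the plan requires no rate by sex.

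**The case against.** The case against has several parts, and much of it stands.

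- A reader might infer that a materially higher event rate in women would usually go unreported. The numbers do not support that in general. At 8% overall it is true only for risk ratios below about 1.75; a doubling triggers reporting in 64–66% of trials and a 2.5-fold excess in 82–85%. The documents do not say which difference is material.
- A reader might infer that no sex-specific estimate appears without the trigger. That is not so. The univariate models in SAP 10.4.5.1 name gender and do not depend on the Fisher result, and the model in SAP 10.4.4.3 may not either. An odds ratio for sex is therefore planned. It does not supply the rate in women.
- A reader might infer that non-significance will be taken as similarity between the sexes. The SAP says a non-significant result supports pooling only for sites (10.4.4.1) and regions (10.4.4.2), not for sex.
- A reader might infer that the protocol promises outcome rates by sex. The sentence on the guidance in Protocol 5.0 is framed around adequate representation, and what follows is an enrolment target.
- The 0.15 threshold is already liberal, and safety is analysed in the SP, which may exceed 330. Using 367 changes the probabilities by only one to three points.

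What remains is the narrower point: the absolute rates and intervals for each sex depend on a p-value, and nothing else in the plan requires them.

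**Conclusion.** The point holds in this limited form. SAP 10.4.4.3 gates the per-sex rates and intervals, and the gate would often stay closed for moderate differences: about 65% of the time for a 1.5-fold excess of Primary AEs in women, 36% for a two-fold excess, and 42% for 50% versus 40% success. When it opens, the estimate tends to be too large. These figures assume 231 men and 99 women, a two-sided Fisher test, a 70:30 split achieved as planned and, for the risk ratios, 8% overall; the differences themselves are assumed. The effect is selective reporting of a secondary result. The primary conclusions are untouched, so this is an inexpensive improvement and not a threat to the trial's claims.

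**What to change.** In SAP 10.4.4.3, delete the p<0.15 condition on reporting. State instead that the primary effectiveness rate (PP) and the Primary AE rate (SP) will be reported for men and for women, with numerators, denominators and exact 95% confidence intervals, whatever the Fisher result. Keep the Fisher p-value as descriptive. State also that the logistic model with sex as a fixed effect is fitted regardless of the test, or say plainly that it is not.

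The cost is one or two SAP sentences and one table. No new data are needed, and the primary tests, significance level and sample size do not change.
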